9.3. Study Days 2-14

The total duration of IV ceftaroline is dependent on the subject's response to therapy but 5-14 days is anticipated in most subjects. If the subject is able to switch to oral drug before Day 15, the procedures outlined for Day 15 (EOIV) should be performed. The rest of the visit schedule will be followed as described in Table 2.1.

- Study Drug Administration:

IV ceftaroline fosamil **15 mg/kg** (or 600 mg if > 40 kg) infused over 120 (\pm 10) minutes q8h (\pm 1 hour) for children **2 years of age – 17 years** of age (inclusive).

IV ceftaroline fosamil **10 mg/kg** infused over 120 (\pm 10) minutes q 8h (\pm 1 hour) for children from **1 year of age to < 2 years** (inclusive) until the subject transitions to oral therapy.

- Clinical Assessments – any time during study day (assessments will be performed for research unless they are already being performed per standard of care; exceptions are indicated):
 - Record concomitant medications (Section 8.3). For subjects who are being breast fed, record all medications taken by the lactating mother.
 - Record resting vital signs (pulse, blood pressure, and respiratory rate), and highest postdose temperature measured.
 - Record adjunctive therapeutic procedures (eg, surgeries).
 - Record standard of care radiology results.
 - Evaluate and record physical findings of hematogenous SA osteomyelitis (eg, warmth, tenderness, swelling, erythema, and movement of the infected extremity). Most of the subjects are expected to have surgical incision and drainage procedures and thus assessing the extremity for swelling, erythema, warmth and tenderness may not be possible because of drains in place and large surgical dressings that cannot be removed. The degree of the subject's ability to ambulate will be assessed if the osteomyelitis is in the lower extremity- ie. walks unaided, able to bear weight, can walk aid using a walker, etc. The use of upper and lower extremities will be assessed in terms of movement and range of motion.
 - Identify, assess, and record any new or ongoing AEs or SAEs
- Laboratory Assessments – any time during the study period if clinically indicated (assessments will be performed for research unless they are already being performed per standard of care; exceptions are indicated):
 - Collect CRP and ESR lab results, if clinically indicated.
 - Collect CBC with differential, BUN, and Creatinine, lab results, if clinically indicated.
 - Obtain blood sample for Alkaline Phosphatase, Bilirubin, AST and ALT, if clinically indicated.
 - If clinically indicated, estimate CrCl using the updated Schwartz "bedside" formula (Schwartz et al, 2009).
 - Collect results of blood cultures only if conducted per standard of care.

- Collect purulent material from bone only if a procedure is performed for standard of care when possible.
- PK Procedures:
 - Efforts will be made to obtain 1 PK blood sample (approximately 0.6 mL) at steady state from all subjects who received ceftaroline fosamil on Days 2 to 5 of treatment (only one PK sample collected on days 2-5) 4 hours (+/- 30 minutes) after the end of the infusion (before the start of the next infusion). PK samples may be collected after any infusion of ceftaroline fosamil on those days and before oral switch.
 - If purulent material is being obtained from bone or subperiosteal abscesses at surgery or via drainage by interventional radiology, we will attempt to obtain specimens for measurement of ceftaroline concentrations.

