3. Suspected hematogenous SA osteomyelitis in a large bone (upper or lower extremities, pelvis) based on clinical findings and radiology results.
4. One to three sites of osteomyelitis with expectation that transition to oral antibiotics will be likely prior to discharge to complete IV therapy (The second or third site might be contiguous like a proximal tibia and distal femur but could also be at sites unrelated such as a distal femur and pelvic bone).
5. Female subjects who have reached menarche must have a negative urine pregnancy test.
6. Female subjects who have reached menarche and are sexually active must be willing to practice sexual abstinence or dual methods of birth control (eg, condom or diaphragm with spermicidal foam or gel) during treatment and for at least 28 days after the last dose of any study drug.
7. Sufficient IV access to receive medication.

Exclusion Criteria: Subjects must **NOT** meet any of the following exclusion criteria. Septic arthritis contiguous to the site of osteomyelitis is not an exclusion criterion.

1. Received more than 24 hours of IV antibiotics prior to enrollment.
2. More than three bones infected.
3. Disseminated infection or is admitted to the pediatric intensive care unit.
4. Underlying condition (excludes mild eczema or reactive airways disease).
5. Suspected or proven venous thrombosis or concern for endocarditis.
6. Requirement for other reasons for another antibiotic potentially active against organisms commonly causing osteomyelitis in children.
7. Creatinine clearance < 50 mL/min/1.73m² (calculated by the Schwartz formula).
8. AST or ALT > 3 times the upper limit of normal.
9. Neutropenia (<500 neutrophils/mm³).
10. Thrombocytopenia (<50,000 platelets/mm³).
11. Females who are currently pregnant or breast feeding.
12. Hypersensitivity reaction to any Beta-lactam antibiotic.
13. Has had an allergic reaction to ceftaroline in the past.

Safety: Adverse event and serious adverse event monitoring, vital signs and laboratory tests (CBC, BUN, Creatinine, Alkaline Phosphatase, Bilirubin, AST and ALT will be obtained within 24 hours prior to enrollment and weekly during ceftaroline treatment and at the completion of ceftaroline treatment). The Alkaline Phosphatase, Bilirubin, AST/ALT results may not be available prior to enrollment of the patient. We do not anticipate that the AST/ALT concentrations will be > 3 UNL but if they were to be this elevated, the subject will be dropped from the study immediately.

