Record adjunctive therapeutic procedures (if performed i.e. Surgery) ⁶					X		
Standard of Care Radiology Results					X		
Clinical outcome				X		X	X
AEs and SAEs	X	X	X	X	X	X	
CBC with differential ⁷	X		X	X			
Chemistries (BUN, Creatinine, Alkaline Phosphatase, Bilirubin, AST, ALT) ⁷	X		X	X			
CRP and ESR ⁸	X	X	X	X	X	X	
Direct Coombs test	X			X			
Urine pregnancy test ⁹	X					X	
CrCl calculation	X				If Clinically Indicated		
Standard of Care Blood Culture ¹⁰			X				
Blood for PK analyses ¹¹			X				
Standard of Care Purulent Material From Bone ¹²			X				
Drug administration ¹³		X	X	X	X		

Abbreviations: AE = adverse event; CBC = complete blood count; CrCl = creatinine clearance; CRP = C-reactive protein; ESR = erythrocyte sedimentation rate; SAE = serious adverse event.

- 1 Perform baseline assessments within 24 hours before first dose of IV study drug.
- 2 Interval history focusing on the use of the involved extremity. On Month 12 follow up interval problems such as pathologic fractures and growth disturbances will be evaluated only.
- 3 The presence of warmth, tenderness, swelling, erythema, and movement of the infected extremity will be recorded specifically. The circumference of the infected extremity taken at the location of point tenderness will be determined.
- 4 Involved extremity will be assessed as at enrollment, if possible. Most of the subjects are expected to have surgical incision and drainage procedures and thus assessing the extremity for swelling, erythema, warmth and tenderness may not be possible because of drains in place and large surgical dressings that cannot be removed.
- 5 The degree of the subject's ability to ambulate will be assessed if the osteomyelitis is in the lower extremity-i.e. walks unaided, able to bear weight, can walk aid using a walker, etc. The use of upper and lower extremities will be assessed in terms of movement and range of motion.
- 6 Any surgical procedures will be documented and the findings described.
- 7 CBC and chemistries . If not done for SOC, collect samples for research if clinically indicated.
- 8 CRP and ESR will be collected typically as part of standard of care. If not performed for SOC, collect samples for research if clinically indicated.
- 9 Perform test if subject is a female who has reached menarche. If a pregnancy test is positive post baseline, follow reporting requirements in Section 11.1.4.

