IV ceftaroline fosamil **10 mg/kg** infused over 120 (\pm 10) minutes q 8h (\pm 1 hour) for children from **1 year of age to < 2 years** (inclusive).

The following Clinical and Laboratory Assessments for Study Day 1 do not need to be repeated if dosing of study medicine is done on the same day as the baseline visit:

- Clinical Assessments - after at least 1 dose of IV study drug (assessments will be performed for research unless they are already being performed per standard of care; exceptions are indicated):
 - o Record concomitant medications (Section 8.3). For subjects who are being breast fed, record all medications taken by the lactating mother.
 - o Record resting vital signs (pulse, blood pressure, and respiratory rate), and highest postdose temperature measured.
 - o Record adjunctive therapeutic procedures (eg, surgeries).
 - o Record standard of care radiology results.
 - o Evaluate and record physical findings of hematogenous SA osteomyelitis (eg, warmth, tenderness, swelling, erythema, and movement of the infected extremity). Most of the subjects are expected to have surgical incision and drainage procedures and thus assessing the extremity for swelling, erythema, warmth and tenderness may not be possible because of drains in place and large surgical dressings that cannot be removed. The degree of the subject's ability to ambulate will be assessed if the osteomyelitis is in the lower extremity-i.e. walks unaided, able to bear weight, can walk aid using a walker, etc. The use of upper and lower extremities will be assessed in terms of movement and range of motion.
 - o Identify, assess, and record any new or ongoing AEs or SAEs
- Laboratory Assessments - after at least 1 dose of IV study drug (assessments will be performed for research unless they are already being performed per standard of care; exceptions are indicated)
 - o If clinically indicated, calculate CrCl using the updated Schwartz "bedside" formula (Schwartz et al, 2009).
 - o Collect results of blood cultures only if conducted per standard of care.
 - o Collect purulent material from bone only if a procedure is performed for standard of care.

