to have surgical incision and drainage procedures and thus assessing the extremity for swelling, erythema, warmth and tenderness may not be possible because of drains in place and large surgical dressings that cannot be removed. The degree of the subject's ability to ambulate will be assessed if the osteomyelitis is in the lower extremity- ie. Walks unaided, able to bear weight, can walk aid using a walker, etc. The use of upper and lower extremities will be assessed in terms of movement and range of motion.

- o Assess clinical outcome (site of infection has complete resolution of pain, swelling and warmth and the patient is able to use the affected extremity normally and is back to normal activities).
- o Identify, assess, and record any new or ongoing AEs or SAEs. Subjects will likely remain in the hospital for less than 24 hours once they are transitioned to oral therapy as per standard of care.
- Laboratory Assessments- any time during study day, but before starting PO drug, if applicable. If these assessments are performed within 48 hours of latest results, do not repeat these assessments (assessments will be performed for research unless they are already being performed per standard of care; exceptions are indicated):
 - o Collect CRP and ESR lab results.
 - o Collect CBC with differential, BUN, and Creatinine.
 - o Obtain blood sample for AST, ALT, Alkaline Phosphatase, Bilirubin and Direct Coombs.
 - o If clinically indicated, estimate CrCl using the updated Schwartz "bedside" formula (Schwartz et al, 2009).
 - o Collect results of blood cultures for *S. aureus* only if conducted per standard of care.
 - o Collect purulent material from bone only if a procedure is performed for standard of care when possible.

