12.4. Safety Analysis

Adverse event and serious adverse event monitoring, vital signs and laboratory tests (CBC, BUN, Creatinine, Bilirubin, Alkaline Phosphatase, AST and ALT will be obtained within 24 hours prior to enrollment and weekly during ceftaroline treatment and at the completion of ceftaroline treatment). The Alkaline Phosphatase, Bilirubin, AST/ALT results may not be available prior to enrollment of the patient.

We do not anticipate that the AST/ALT concentrations will be > 3 UNL but if they were to be this elevated, the patient subject will be dropped from the study immediately.

Safety parameters include AEs, SAEs, deaths, clinical laboratory parameters (eg, hematology parameters, chemistry parameters), and vital signs. For each safety parameter, the last assessment made before the first dose of IV study drug will be used as the baseline for all analyses.

The incidences of TEAEs, SAEs, deaths, and discontinuations due to AEs will be summarized by system organ class and preferred term according to the Medical Dictionary for Regulatory Activities by relationship to the study drug, and by severity.

Descriptive statistics of observed results and the change from baseline will be presented for clinical laboratory results, and vital signs. The incidence of PCS laboratory results will be summarized.

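### Five of the nine off-study rules need laboratory values during ceftaroline, but the protocol gives conflicting schedules for those labs and requires CrCl only at baseline

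*Combined protocol and SAP*

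**What the plan says.** **The stop rules.** Section 7.7.1 lists nine reasons for taking a child off study. Five rest on laboratory results: estimated CrCl below 50, absolute neutrophil count below 500, hemolytic anemia of Grade 2 or above (a hemoglobin fall of more than 2 g), platelets below 100,000, and AST/ALT above 3 x ULN. Section 8.5 repeats the CrCl rule, and Section 10.9 adds that the DRC should be contacted.

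**Labs during ceftaroline, unconditional version.** The Safety paragraph of the Summary says CBC, BUN, creatinine, alkaline phosphatase, bilirubin, AST and ALT are obtained before enrollment and "weekly during ceftaroline treatment and at the completion of ceftaroline treatment". Section 12.4 says the same: these tests "will be obtained within 24 hours prior to enrollment and weekly during ceftaroline treatment and at the completion of ceftaroline treatment".

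**Labs during ceftaroline, conditional version.** Section 9.3 (Days 2-14) says "Collect CBC with differential, BUN, and Creatinine, lab results, if clinically indicated" and "Obtain blood sample for Alkaline Phosphatase, Bilirubin, AST and ALT, if clinically indicated". Section 9.8.1, which lists the study-required tests, asks for AST/ALT only at baseline and at EOIV. Section 9.8.2 has hemoglobin, WBC, platelets, BUN and creatinine recorded only when they are done for standard of care.

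**The Schedule.** Section 10.9 refers clinical laboratory tests to the Schedule of Assessments. Table 1.1 marks CBC and chemistries with an X on Days 2-14, but footnote 7 qualifies the mark: "If not done for SOC, collect samples for research if clinically indicated". The first sentence of that footnote looks incomplete in the extracted text.

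**CrCl.** The estimate is unconditional at baseline (9.1). After that it is conditional: on Day 1, "If clinically indicated, calculate CrCl using the updated Schwartz" (9.2); on Days 2-14, "If clinically indicated, estimate CrCl using the updated Schwartz" (9.3), with the same condition at EOIV (9.4). The CrCl row of Table 1.1 agrees.

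**EOIV.** Section 9.4 requires CBC, creatinine, AST and ALT, subject to a waiver: "If these assessments are performed within 48 hours of latest results, do not repeat these assessments".

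**The concern.** The five rules are mandatory stops in a trial whose primary objective is safety, and the Statistics paragraph of the Summary singles out bone marrow suppression for evaluation. A stop rule works only if the value it is written on is obtained while treatment continues. Under 9.3 that depends on someone judging a test to be indicated. A falling neutrophil count or a moderate creatinine rise can be silent, so the absence of an indication does not show that the rule is not met.

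The renal rule has a further gap. Making creatinine weekly would not by itself make anyone compute CrCl, because the calculation is conditional at every visit after baseline, even with a creatinine in hand. The protocol itself gives grounds to care: it describes urinary excretion as the principal elimination route (4.2.4) and names the kidney as a potential target of toxicity in animals (4.2.1).

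What is at stake is timing. EOIV assessments fall within 24 hours after the last IV dose (9.4), so a breach first seen there cannot stop ceftaroline.

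**Working it through.** The protocol states no figure on this point to reproduce. The check is a count of rules, a comparison of schedules, and two short calculations.

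**1. Rules that need a laboratory value.** Of the nine in 7.7.1, four are clinical (home parenteral therapy, return to IV after the oral switch, diarrhea with blood or mucus, rash). The other five need creatinine with the CrCl calculation (1), CBC with differential (3: neutrophils, hemolytic anemia, platelets) or transaminases (1). So 5 of 9.

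**2. What is required, by source.**

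| Source | CBC, creatinine on Days 2-14 | AST/ALT on Days 2-14 |
|---|---|---|
| Summary, 12.4 | weekly | weekly |
| 9.3 | conditional | conditional |
| 9.8.1 | not listed | not required (baseline and EOIV only) |
| 9.8.2 | recorded if done for care | not listed |
| Table 1.1 | X, qualified by footnote 7 | X, qualified by footnote 7 |

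Section 10.9 points to Table 1.1, and Table 1.1 points back to clinical indication. The reference therefore does not settle the matter.

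**3. Required draws and doses between them.** Assumptions: q8h dosing gives 3 doses a day; weekly means every 7 days from Day 1, so the first on-treatment draw is about Day 8; no labs are drawn for care. The longest run of doses without a required lab is 3 x days under 9.3, and the smaller of 3 x days and 3 x 7 = 21 under 12.4.

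| IV course | Required draws between baseline and EOIV: 9.3 / 12.4 | Longest run of doses: 9.3 / 12.4 |
|---|---|---|
| 5 days | 0 / 0 | 15 / 15 |
| 7 days | 0 / 0 | 21 / 21 |
| 10 days | 0 / 1 | 30 / 21 |
| 14 days | 0 / 1 | 42 / 21 |

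The two schedules differ only on courses longer than 7 days, and then by one draw on courses up to 14 days.

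**4. How large a creatinine rise meets the renal rule.** The formula in 9.1 is CrCl = 0.413 x height / creatinine. Height is effectively fixed within a child over the IV course, so creatinine at the limit divided by baseline creatinine equals baseline CrCl / 50. For illustrative baselines:

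- 60: 60/50 = 1.2-fold
- 75: 75/50 = 1.5-fold
- 100: 100/50 = 2.0-fold
- 150: 150/50 = 3.0-fold

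The creatinine that corresponds to 50 also depends on height (0.413 x height / 50): 0.62 mg/dL at 75 cm, 0.91 at 110 cm, 1.16 at 140 cm and 1.40 at 170 cm. A raw creatinine is therefore not easily read against the rule without the calculation. Required CrCl calculations after baseline: 0 at every visit.

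**The case against.** The strongest reply is that the gap is small in practice. Home parenteral therapy takes a child off study (4.5, 7.7.1), so study ceftaroline is inpatient treatment, and 9.8.2 expects CBC and creatinine results from care. Children with underlying conditions are excluded, other nephrotoxic agents are prohibited (7.5), and a rule written on estimated CrCl implies that someone will estimate it when creatinine rises. On courses of 7 days or less the two schedules require the same labs. All of this stands and limits the size. It does not remove the conflict: the sponsor wrote mandatory stops and an unconditional weekly schedule, and the visit instructions drop the requirement to check.

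A second reply is that 9.3, 9.8.1, 9.8.2 and footnote 7 agree with one another, so the weekly sentence is the outlier. That is fair. The documents do not establish which version was intended. The case for weekly is that it is already in the protocol and is the version that serves the stop rules; it is not that 9.3 is demonstrably the error.

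Three stronger readings are tempting, and none is supported:

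- *The end-of-IV safety data are compromised.* They are not. Section 9.4 requires CBC, creatinine and AST/ALT at EOIV (or accepts results from within 48 hours), and the primary endpoint is safety at the end of IV therapy. No estimate, population or test is shown to change.
- *Children will go up to 42 doses unmonitored, or stops will be missed.* The 42-dose figure assumes no care labs at all. The documents give neither a probability of a missed case nor a distribution of IV durations.
- *Nothing in the protocol says which schedule governs.* Section 10.9 does name the Schedule of Assessments. The difficulty is that the Schedule's own footnote restores the condition, and its opening sentence may have lost words in extraction.

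**Conclusion.** The point holds as an inconsistency in the assessment schedule that bears on patient safety. Five of nine off-study rules depend on labs that two parts of the protocol require weekly and that 9.3, 9.8.1, 9.8.2 and footnote 7 leave conditional, unrequired or dependent on care. The renal rule need never be evaluated on drug, because CrCl is compulsory only at baseline.

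The severity is modest. Resolving the schedule in favor of 12.4 adds one required draw, about Day 8, on courses of 8-14 days and none on courses of 7 days or less. On the shorter courses the only gain is that CrCl is computed whenever a creatinine exists. The benefit is earlier detection, while ceftaroline can still be stopped. The draw count assumes that weekly means every 7 days from Day 1; the creatinine multiples use illustrative baselines, not values expected in this population.

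**What to change.** **(a) One schedule.** In 9.3, 9.8.1, 9.8.2 and Table 1.1 footnote 7, state the 12.4 schedule for CBC with differential, creatinine and AST/ALT: weekly during ceftaroline and at completion, using results drawn for care when they exist. Changing 9.3 and the footnote alone would leave 9.8.1 and 9.8.2 contradicting 12.4.

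**(b) Automatic CrCl.** In 9.2-9.4 and Table 1.1, have the eCRF derive CrCl from baseline height whenever a creatinine is recorded during ceftaroline or at EOIV, and flag values below 50 mL/min/1.73m². The stopping limits do not change. As an editorial matter, 7.7.1, 8.5 and 10.9 could give the limit in the same unit as the formula.

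**Cost.** Wording edits, one eCRF calculation from data already recorded, and about one research draw per child on 8-14 day courses when none is done for care. If all 18 children had such courses and no care labs, that is 18 x 1 = 18 draws. This is not a strict ceiling, because the protocol only anticipates 5-14 days in most subjects and a longer course could need another draw. The 48-hour waiver in 9.4 limits duplication at EOIV. Sample size, endpoints and analysis populations are unaffected.

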9.4. Study Day 15 (End of IV Treatment-EOIV)

The total duration of IV ceftaroline is dependent on the subject's response to therapy but 5-14 days is anticipated in most subjects. If the subject is able to switch to oral drug before Day 15, these procedures may be performed before Day 15. Conduct EOIV assessments within 24 hours after administration of the last dose of IV study drug (subjects will likely remain in the hospital for less than 24 hours once they are transitioned to oral therapy as per standard of care) or at time of premature discontinuation of study drug or early withdrawal from study (if on IV study drug). Conduct the EOIV assessments in place of the regular study visit assessments that would have been performed the day of that visit. A subject may be eligible to switch to PO drug on or after Study Day 3 (Section 9.2). EOIV assessments must occur before starting PO drug. The rest of the visit schedule should be followed as described in Table 2.1.

If applicable, as IV study drug may or may not be given on the same calendar day as EOIV assessments, administer IV study drug IV ceftaroline fosamil **15 mg/kg** (or 600 mg if > 40 kg) infused over 120 (\pm 10) minutes q8h (\pm 1 hour) for children **2 years of age – 17 years** of age (inclusive).

IV ceftaroline fosamil **10 mg/kg** infused over 120 (\pm 10) minutes q 8h (\pm 1 hour) for children from **1 year of age to < 2 years** (inclusive) until the subject transitions to oral therapy.

- Clinical Assessments - any time during study day, but before starting PO study drug, if applicable (assessments will be performed for research unless they are already being performed per standard of care; exceptions are indicated):
 - Record concomitant medications (Section 8.3). For subjects who are being breast fed, record all medications taken by the lactating mother.
 - Record vital signs: resting pulse, blood pressure, and respiratory rate; and highest daily temperature measured.
 - Record adjunctive therapeutic procedures (eg, surgeries).
 - Record standard of care radiology results.
 - Evaluate and record physical findings of hematogenous SA osteomyelitis (eg, warmth, tenderness, swelling, erythema, and movement of the infected extremity). Most of the subjects are expected

to have surgical incision and drainage procedures and thus assessing the extremity for swelling, erythema, warmth and tenderness may not be possible because of drains in place and large surgical dressings that cannot be removed. The degree of the subject's ability to ambulate will be assessed if the osteomyelitis is in the lower extremity- ie. Walks unaided, able to bear weight, can walk aid using a walker, etc. The use of upper and lower extremities will be assessed in terms of movement and range of motion.

- o Assess clinical outcome (site of infection has complete resolution of pain, swelling and warmth and the patient is able to use the affected extremity normally and is back to normal activities).
- o Identify, assess, and record any new or ongoing AEs or SAEs. Subjects will likely remain in the hospital for less than 24 hours once they are transitioned to oral therapy as per standard of care.
- Laboratory Assessments- any time during study day, but before starting PO drug, if applicable. If these assessments are performed within 48 hours of latest results, do not repeat these assessments (assessments will be performed for research unless they are already being performed per standard of care; exceptions are indicated):
 - o Collect CRP and ESR lab results.
 - o Collect CBC with differential, BUN, and Creatinine.
 - o Obtain blood sample for AST, ALT, Alkaline Phosphatase, Bilirubin and Direct Coombs.
 - o If clinically indicated, estimate CrCl using the updated Schwartz "bedside" formula (Schwartz et al, 2009).
 - o Collect results of blood cultures for *S. aureus* only if conducted per standard of care.
 - o Collect purulent material from bone only if a procedure is performed for standard of care when possible.

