5.2. Secondary Objectives

- Evaluate efficacy of ceftaroline in pediatric subjects with acute hematogenous osteomyelitis at the end of IV therapy, at the end of total therapy (anticipated to be at 4 to 6 weeks after enrollment), and at one year after enrollment.
- Evaluate clearance of *S. aureus* bacteremia if blood cultures initially positive.
- Assess proportion of patients with plasma levels of ceftaroline that exceed 1 µg/mL for over 60% of a dosing interval.

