6.1. Outcome Measures

Primary: Safety evaluations will be conducted in the children who have started treatment with ceftaroline. Assessments will include:

- AEs, SAEs, deaths, and discontinuations due to SAEs.
- Vital signs and laboratory parameters.

Secondary:

- Clinical response (the subject has been afebrile for at least 48 hours, has negative blood cultures, is clearly improving in general, is able to eat and drink, and is able to use or move the involved extremity) at the end of parenteral therapy (approximately days 5 to 14) by subject and by baseline pathogens although *S. aureus* is expected to be the predominant pathogen.
- Clinical outcome (site of infection has complete resolution of pain, swelling and warmth and the patient is able to use the affected extremity normally and is back to normal activities) at the EOT and at the one year follow up visit.

- Clinical relapse within a year of enrollment in the study or the development of a pathologic fracture.

PK:

- Concentrations of ceftaroline fosamil, ceftaroline, and ceftaroline M-1 in plasma.
- If available, concentrations of ceftaroline fosamil, ceftaroline, and ceftaroline M-1 in purulent material such as bone or subperiosteal abscess or synovial fluid.

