12.3. Secondary Endpoints

1. Successful treatment of acute hematogenous osteomyelitis at one year after completion of a 4 to 6 week total antibiotic treatment and at one year after enrollment.
2. Clearance of *S. aureus* bacteremia if blood cultures initially positive.
3. The proportion of children with plasma concentrations of ceftaroline that exceed 1 μ g/mL for over 60% of a dosing interval.

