12.5. Efficacy Analysis

- Clinical response by subject and by baseline pathogen at the conclusion of IV ceftaroline.
- Clinical outcome at the completion of total therapy (IV plus oral)
- Clinical outcome at one year after enrollment into study long-term follow-up.

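### Section 9.4 has the site record complete resolution at the end of IV therapy, but Sections 6.1 and 12.5 make five-part clinical response the efficacy measure there

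*Combined protocol and SAP*

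**What the plan says.** Section 5.2 sets out to evaluate efficacy in children "with acute hematogenous osteomyelitis at the end of IV therapy, at the end of total therapy", and at one year.

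Section 6.1 defines two measures for this:
- **Clinical response**, at the end of IV therapy. It has five components: no fever for at least 48 hours, negative blood cultures, clear general improvement, oral intake, and limb use. The last component and the timing read "is able to use or move the involved extremity) at the end of parenteral therapy (approximately days 5 to 14) by subject".
- **Clinical outcome**, which is complete local resolution with normal limb use. Its wording ends "back to normal activities) at the EOT and at the one year follow up visit".

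Section 12.5 keeps this split and lists "Clinical response by subject and by baseline pathogen at the conclusion of IV ceftaroline".

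The visit instructions differ. At EOIV, Section 9.4 says "Assess clinical outcome (site of infection has complete resolution of pain, swelling and warmth", and goes on to require normal limb use and normal activities. Table 1.1 has a row "Clinical outcome" marked at EOIV, EOT and follow-up, and no row for clinical response. Section 9.4 also warns that "assessing the extremity for swelling, erythema, warmth and tenderness may not be possible because of drains in place and large surgical dressings".

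Section 12.3 begins its list of secondary endpoints with "Successful treatment of acute hematogenous osteomyelitis at one year after completion of a 4 to 6 week total antibiotic treatment", adds one year after enrollment, and names neither EOIV response nor outcome at the end of total therapy.

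Section 7.8.2 classes children stopped for insufficient effect as failures. Section 7.8.1 (SAE with other antimicrobials needed) and Section 7.8.3 (withdrawal) create an indeterminate category. Section 12.5 gives no denominator. Section 12.8 says only that data are assessed until the child is dropped and that missing data are noted.

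**The concern.** Efficacy at the end of IV therapy is the first time point in the first secondary objective, and it is the time point closest to the effect of ceftaroline itself, since oral drugs follow. A site that follows Section 9.4 to the letter enters a complete-resolution judgement at that visit. The analyst who follows Section 12.5 then needs a five-component response that no visit instruction asks for by name.

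Two consequences follow. The entry made at EOIV may be reported as the response, although it measures something else. Alternatively, response is rebuilt afterwards from scattered entries without a stated derivation. In either case, the handling of children without a clear result would be decided after an open-label study's data are known.

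**Working it through.** **1. The two definitions side by side.**

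| Element | Response (6.1, 12.5) | Outcome as written in 9.4 | Separate EOIV record in 9.4 |
|---|---|---|---|
| Fever | none for at least 48 h | not mentioned | highest daily temperature |
| Blood cultures | negative | not mentioned | results, if done as standard of care |
| General condition | clearly improving | not mentioned | no explicit item |
| Oral intake | able | not mentioned | no explicit item |
| Limb | use or movement | normal use | movement, range of motion, ambulation |
| Pain, swelling, warmth | not required | complete resolution | physical findings, where visible |
| Activities | not required | normal | none |

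The only shared element is the limb, and there the standards differ (some use or movement against normal use). A child who does not meet the 9.4 item may or may not be a responder. A child who meets it has not thereby been shown to be afebrile, culture-negative or eating. Response cannot be read off the 9.4 item in either direction.

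**2. Fit of the 9.4 item to the visit.** EOIV assessments come before oral drug starts, and the section expects children to go home less than 24 hours after the switch. Normal activities are therefore being judged at about the time of hospital discharge. Most children are expected to have had surgical drainage, and by the section's own account swelling and warmth may then not be assessable.

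**3. How much of response can be recovered.** Three of the five components (temperature, limb movement, standard-of-care cultures) have a record at EOIV. Two (general improvement, oral intake) have no explicit item. For children switched to oral drug, Section 6 lists the same five conditions for the switch, so response largely follows from the switch decision. For children stopped for lack of effect, Section 7.8.2 gives failure.

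**4. Children without a clear status.**
- Section 7.8.1 labels some children indeterminate, but neither 12.5 nor 12.8 says whether they stay in the denominator.
- Section 7.8.3 asks for EOIV assessments on the day of withdrawal if possible, and applies the indeterminate label to subsequent time points. The status at an EOIV assessment done that same day is not explicit.
- Children who need home IV therapy are assessed for outcome at discharge (4.5) and have EOIV assessments (7.8.1), with no stated definition or label.

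**5. Size.** With 18 treated children (6.2, 7.9), one child moves an all-treated proportion by 1/18 = 0.056, or 5.6 percentage points. The documents give no rate of indeterminate children. As an assumption, let m of 18 be indeterminate and all others respond. The assessable-only result is then always 100%, and the all-treated result is (18 − m)/18:
- m = 0: 18/18 = 100%
- m = 1: 17/18 = 94.4%
- m = 2: 16/18 = 88.9%
- m = 3: 15/18 = 83.3%
- m = 4: 14/18 = 77.8%

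For m = 2 the exact 95% intervals are 65.3 to 98.6% for 16/18, and 79.4 to 100% for 16/16.

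**6. The plan's own figure.** The stated N reproduces. With π = 0.50 against 0.80, the smallest n with exact one-sided type 1 error at most 0.05 and power at least 0.80 is 18, with success declared at 13 or more (error 0.0481, power 0.867). Section 6.2 does not say which endpoint π describes, so nothing here bears on that figure.

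**The case against.** The strongest reply is that this is template carry-over. The same complete-resolution sentence appears in Sections 9.4, 9.5, 9.6 and 9.7, Section 7.8 uses clinical outcome as a general label, and the raw material for response is mostly collected. The efficacy analysis is descriptive, Section 12.5 names no statistic, and decisions in Sections 7.10 and 12.7 turn on treatment failures rather than on a response proportion.

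Much of this stands, and it limits the weight of the point. It does not remove the contradiction: Section 9.4 does not use a loose label but writes out the definition that Section 6.1 places at EOT and one year. Carry-over would explain the error, but the site would still follow the text.

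A reader might infer more than the documents support:
- **That most ways of leaving IV drug have no status.** Section 9.4 requires EOIV assessments at premature discontinuation or early withdrawal while on IV drug. Section 7.8.2 settles the failures. Section 7.8.3 covers withdrawal by the investigator for reasons other than an SAE, which is the natural place for non-SAE removals under Section 7.7.1. The gap is narrower: the counting of indeterminate children, and the EOIV status of home-IV children and of same-day withdrawals.
- **That the power of the trial is eroded.** This would need π in Section 6.2 to be EOIV response, which is not stated.
- **That response is lost.** It is partly recoverable, and largely so on the intended oral-switch pathway.

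**Conclusion.** The contradiction is real and should be fixed. Section 9.4 and Table 1.1 schedule complete-resolution clinical outcome at EOIV, where Sections 6.1 and 12.5 call for five-component clinical response. How far results under the two definitions would differ cannot be computed from the documents.

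The missing counting rule is a lesser point, largely one of absent detail. It is worth 5.6 percentage points per child on an all-treated proportion. That figure assumes that EOIV response is reported as a proportion of 18 treated children, which Section 12.5 implies but does not state. The illustration with m indeterminate children rests on assumed counts.

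The measure is secondary and descriptive. The primary safety analysis and N = 18 are not affected.

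**What to change.** 1. In Section 9.4 and the EOIV entry of Table 1.1, replace complete-resolution clinical outcome with the Section 6.1 clinical response. Record each of the five components as met, not met or not assessable, for every child at the EOIV assessment that Section 9.4 already requires, including at premature discontinuation or withdrawal. Keep complete resolution at EOT and one year.
2. In Section 12.5, report EOIV response over all treated children, with failures, indeterminate and unassessable children shown separately and the assessable-only proportion beside it. State the EOIV status of home-IV children and of children withdrawn that day.
3. Align Section 12.3 with Sections 5.2, 6.1 and 12.5 for both EOIV response and outcome at the end of total therapy. Adding EOIV response alone would leave the end-of-therapy outcome missing.

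The cost is wording in four places (9.4, Table 1.1, 12.3, 12.5) and about five eCRF entries at an existing visit, with no new blood draw or procedure. The downside is a possibly less favourable all-treated proportion, shown next to the assessable-only one.
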